Patients will receive brochures for each medication class that they are prescribed, with subsequent brochures being mailed out 3 months after the previous one. We anticipate that less than 10% of participants are on 2 or more CNS medication classes. Additionally, we will mail all participants an antihistamine brochure because there is high utilization of over-the-counter antihistamine use, but prescriptions in automated data sources is low.

No other follow-up is conducted by the study team until it is time to pull automated patient data to measure outcomes as described in this application.

c. Flow diagram (if needed)

If the study design is complicated (i.e., has multiple populations, data sources, subject pathways, etc.), insert a flow diagram here or upload it as a separate document if the format is incompatible with this form.

NOTE: Update March 2021 - Due to initial delays due to COVID 19 and changes to procedures based on feedback from our intervention clinics (during both the first two recruitment waves and during our study overview sessions at clinics), our overall study time is going to be delayed significantly including pulling participants and collecting outcomes data, therefore we need to extend the date range for both sample identification and data collection by 1 year. This only applies to PHASE III (Study Intervention): The intervention will be rolled out monthly to clinics and persist for 12 months as depicted in the table below.

Clinic	Apr-2021	May-2021	Jun-2021	Jul-2021	Aug-2021	Sep-2021	Oct-2021	Nov-2021	Dec-2021	Jan-2022	Feb-2022	Mar-2022	Apr-2022	May-2022	Jun-2022	Jul-2022
1	x	x	x	x	x	x	x	x	x	x	x	x				
2		x	x	x	x	x	x	x	x	x	x	x	x			
3		x	x	x	x	x	x	x	x	x	x	x	x			
4			x	x	x	x	x	x	x	x	x	x	x	x		
5				x	x	x	x	x	x	x	x	x	x	x	x	
6				x	x	x	x	x	x	x	x	x	x	x	x	
7			x	x	x	x	x	x	x	x	x	x	x	x		
8					x	x	x	x	x	x	x	x	x	x	x	x
9					x	x	x	x	x	x	x	x	x	x	x	x

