Patients will be excluded for any one of the following: a) diagnosis of dementia/Alzheimer's disease or a pharmacy dispensing for a medication(s) used to treat dementia (i.e., a cholinesterase inhibitor or memantine); b) reside in a skilled nursing facility; c) cancer diagnosis in the prior 12 months; d) receiving hospice or palliative care; e) legally blind (unable to see print materials); f) unable to read English (unable to understand and comment on the print materials); g) unable to hear and/or speak English (unable to hear focus group questions and respond); h) unavailable at the date/time of the focus group, i) lacking transportation to get to and from the focus group and j) uncomfortable or unwilling to participate in a group discussion.

After inclusion and exclusion criteria are applied for the focus group sample, we will select a random-weighted sample (weighted on age, sex, and race/ethnicity) of 400 potential participants. Phase II work was completed in 2019

Phase III (Trial) Exclusion Criteria:

For the opt-out protocol (July 2020-October 2020)

Individuals will be excluded for any one of the following: a) diagnosis of dementia/Alzheimer's or a pharmacy dispensing for a medication(s) used to treat dementia (i.e., a cholinesterase inhibitor or memantine), b) reside in a skilled nursing facility; c) metastatic cancer diagnosis in the prior 12 months; e) receiving hospice or palliative care; f) legally blind (unable to read print materials); g) indication in the KPWA VDW demographics table that the patient requires a translator (cannot read materials printed in English); h) enrolled in SMART (IRBnet 1220346, PI [name]) or STRIPE (IRBnet 1295096, PI [name]); i) enrolled in KPWA COMET initiative; a pharmacy based initiative to lower opioid dosing.

For the waiver of consent protocol (December 2020-):

Individuals will be excluded for any one of the following: a) diagnosis of dementia/Alzheimer's or a pharmacy dispensing for a medication(s) used to treat dementia (i.e., a cholinesterase inhibitor or memantine), b) reside in a skilled nursing facility; c) metastatic cancer diagnosis in the prior 12 months; e) receiving hospice or palliative care; f) legally blind (unable to read print materials); g) indication in the KPWA VDW demographics table that the patient requires a translator (cannot read materials printed in English); h) enrolled in SMART (IRBnet 1220346, PI [name]) or STRIPE (IRBnet 1295096, PI

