5.1 Screening Activities

Will you conduct screening or any other research procedures before obtaining informed consent for the main study activities?

☒ **YES** ☐ **NO**

If YES, briefly describe any data collection/screening or other research procedures that you will use to determine eligibility in the study (e.g., phone screening, chart abstraction, blood tests, wearing activity devices, attending office visits, etc.) before obtaining full informed consent. Also complete the table below.

Brief Description: | **Phase II (Focus Group):** Prior to obtaining Informed consent from focus group participants, our KPWHRI study programmer accessed KPWA automated data to assemble our sample of potentially eligible Phase II focus group participants (N=400). We

mailed focus group invitation letters to this group and eligibility was confirmed by Survey Phone Room during a brief phone screening. We expected approximately 10% of potential subjects will participate (N~40) in the 3 focus groups. Phase II work was completed in 2019.

Phase III (Trial):

In this application we describe the procedures for the Opt-Out Protocol (July 2020-October 2020) group and the Waiver of Consent/HIPAA Authorization Protocol (December 2020-) group.

The “Opt-Out Protocol (July 2020-October 2020)” refers to the participants who were recruited during the period of July 2020 until October 2020. During that time, the opt-out rate from the intervention arm was approximately 15% and the study team put recruitment on pause as they worked with the biostatistician to determine if this rate was a fatal flaw, which it turned out to be. At this time, the study team made the decision to change procedures by asking for a waiver of HIPAA authorization and consent for both intervention arm and regular care participants. No participants were enrolled until the waiver requests are granted.

The “Waiver of Consent/HIPAA Authorization Protocol (December 2020-) group” refers to the participants who will be enrolled after the modification for a waiver of HIPAA authorization and consent is granted.

Opt-Out Protocol (July 2020-October 2020)

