We are requesting a waiver of documentation of consent for Phase III trial (intervention) activities. Prior to receiving the Study Information Sheet, our KPWHRI study programmer will access KPWA automated data (VDW) and use lists of participants enrolled in the STRIPE and SMART studies and enrolled in COMET, to assemble our sample of Phase III participants. There is no further screening for eligibility or primary data collection. Patients receiving care in clinics assigned to the Intervention Group will be mailed a Study Information Sheet with their first patient brochure. The Information Sheets provide an opt out number to call if patients prefer to not have their data included in the study or they do not want to receive patient brochures. |

Waiver of Consent/HIPAA Authorization Protocol (December 2020-)We are requesting a waiver of consent for Phase III trial (intervention) activities consisting of both regular care and intervention arm participants. A KPWHRI study programmer will access KPWA automated data (VDW), and use lists of participants enrolled in the STRIPE and SMART studies and enrolled in COMET, to assemble our sample of Phase III participants. There is no further screening for eligibility or primary data collection. Patients receiving care in clinics assigned to the Intervention Group will be mailed a notification letter about the research study occurring in their clinic, patient brochure and self-help information sheets.

Source (specify)	List of primary data collection that will be used to identify and determine eligibility of potential subjects	Date Range(s)
------------------	----------------------------------------------------------------------------------------------------------------------	---------------

(i.e., screening phone survey, activity monitor results, lab tests, etc.)		
Phone screening (for Phase II focus groups only)	See attached screening questions and phone script	n/a

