5.3 Screening Data

Describe the plan for use/destruction of data collected during screening/recruitment in the event of a screen failure or when a potential subject is contacted but refuses participation or does not respond (e.g. destroyed immediately, destroyed at end of study, retained so that subjects are not contacted repeatedly about participation after they have declined, etc.).

Phase II (Focus Group): Potential participants will be called a max of 6 times after the recruitment letter goes out. A tracking database will be used to record the date of the invite letter, date and number of recruitment calls, whether contact was made, screening status, eligibility, active versus passive refusals, participation, and incentives provided. Potential participants who choose to opt-out will be coded as a refusal and no further data will be collected or calls made. Phase II work was completed in 2019.

Phase III (Trial):**Opt-Out Protocol (July 2020-October 2020)**

There is no screening for the trial. Subjects in the Intervention Group that opt out will be removed from the sample, no further data will be collected, and they will not receive the study educational brochures.

Waiver of Consent/HIPAA Authorization Protocol (December 2020-)

There is no screening for the trial. |

6. Informed Consent

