If a participant in Phase III withdraws from the study, we will remove his/her study ID from future data pulls but will keep data previously obtained. This means that although they received the initial brochure, we will not mail future patient brochures (or accompanying EBPOs to their providers) to patients who opt out/withdraw from the study.

Waiver of Consent/HIPAA Authorization Protocol (December 2020-)

Participants will not be able to withdraw from the study. We have included clarifying language in the notification of study letter that they may receive multiple informational brochures and postcards and that they do not have to act on the materials. We have requested a waiver of consent and HIPAA authorization for the collection of the EMR from which participants cannot opt out of.

|

l. Investigator Initiated Withdrawal

Describe any anticipated circumstances under which subjects could be withdrawn from the research without their consent.

| Not applicable for this study. |

m. Orderly Termination

Describe any procedures for orderly termination of the study, if applicable.

| Not applicable |

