- 10) The study team will analyze the focus group data and make changes to patient brochures as necessary.
- 11) All changes to brochures will be sent to the IRB as a modification

Phase II work was completed in 2019

Phase III (Trial):**Opt-Out Protocol (July 2020-October 2020)**

1. In order to ensure that KP providers are not confused by this communication, we will inform providers at the 8 Intervention Clinics about this study and materials that they can expect to receive through morning huddles and/or brown bag lunches as deemed appropriate by the clinic managers.
2. The KPWHRI study programmer creates study sample per our inclusion/exclusion criteria listed above in Section 3.3 and uploads this sample to our study database.
 - a. Sample created on the date the intervention is rolled-out (2 of the 8 clinics rolled out each month) to a particular intervention clinic and the matched usual care clinic
3. The study team mails the information sheet, invitation letter, first brochure, and relevant self-care handout(s) to a subgroup of the Intervention Group from each intervention clinic each month. The Control Group receives nothing.
4. Corresponding EBPOs sent via secure fax to the patient's provider.
5. One month after sending the patient brochure, the study team mails the postcard mailer
6. Repeat process for subsample each month for 12-months.
 - a. Patients (and accompanying materials to their providers) receive only one brochure per medication class during the study period
 - b. Patients taking multiple medication classes of interest will receive no more than one brochure every 3 months for a max of 4 brochures in 12 months.

Extract automated data from table 7.3.d (opt out protocol) from KPWA VDW on Intervention and Control Group to assess outcomes at 24 months post roll-out into the intervention clinic and matched usual care clinic.

Waiver of Consent/HIPAA Authorization Protocol (December 2020-)

1. In order to ensure that KP providers are not confused by this communication, we will inform providers at the 8 Intervention Clinics about this study and materials that they can expect to receive through morning huddles and/or brown bag lunches as deemed appropriate by the clinic managers.
2. The KPWHRI study programmer creates study sample per our inclusion/exclusion criteria listed above in Section 3.3 and uploads this sample to our study database.

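### The plan does not settle the use of the 2020 opt-out cohort, which lost about 15% of one arm, or whether its members may enter the 2021 samples

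*Combined protocol and SAP*

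**What the plan says.** **Opt-out phase.** In July to October 2020, intervention patients were mailed an information sheet with their first brochure. Section 5.1: "The Information Sheets provide an opt out number to call if patients prefer to not have their data included in the study". Control patients were sent nothing (section 7.5), so they had no such route. Section 5.1 reports that "the opt-out rate from the intervention arm was approximately 15" percent. Recruitment was paused while the team worked with the biostatistician "to determine if this rate was a fatal flaw, which it turned out to be", and a waiver of consent was then sought for both arms.

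**Handling of opt-outs.** Section 5.3: "Subjects in the Intervention Group that opt out will be removed from the sample, no further data will be collected". Section 7.1.k: "we will remove his/her study ID from future data pulls but will keep data previously obtained".

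**Outcome data.** The opt-out list in section 7.5 ends with the instruction to "Extract automated data from table 7.3.d (opt out protocol) from KPWA VDW on Intervention and Control Group to assess outcomes at 24 months" after roll-out. Section 7.3.d keeps a separate outcome table for that protocol, closing on 6/30/2022; the waiver-protocol table runs to 9/30/2024. The analysis plan in section 2.2.d does not mention the 2020 cohort.

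**Restart.** Section 2.3.c cites clinic feedback received "during both the first two recruitment waves and during our study overview sessions at clinics" and sets out a schedule in which nine clinics start between April and August 2021. The nine intervention clinics in section 7.1.a include Capitol Hill, which section 5.2.a names as the first clinic. Section 3.3.a draws each sample at roll-out from patients whose dispensings supply 70 or more of the preceding 90 days. The waiver-phase exclusions in section 3.3.b repeat the opt-out list and add an opioid use disorder code. They say nothing of 2020 participation, mailing or refusal. In section 7.1.e the opt-out mailing algorithm leaves out withdrawn patients; the waiver version has no such step.

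**The concern.** Two selection problems arise, both after randomisation and both in the intervention arm only.

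First, patients who opted out chose to leave, and controls had no counterpart choice. If the 2020 data enter the efficacy analysis, the remaining intervention patients are compared with an unselected control group. Adjusting for age, sex and prior falls cannot bring the removed patients back.

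Second, a clinic launched in 2020 and rolled out again in 2021 has its sample defined by current chronic use. A patient who stopped because of the 2020 mailing no longer qualifies, while a comparable patient at the matched control clinic still does. That selects on the effect the intervention is meant to have.

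The plan is also unclear on whether people who refused use of their data in 2020 can be drawn into the 2021 sample, from which section 7.1.k allows no withdrawal.

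**Working it through.** The documents give no power calculation, fall rate or cohort size, so there is no planned figure to reproduce. The inputs are the 15% (section 5.1) and the stated dates. The other quantities are assumptions, marked as such.

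**1. One-arm removal within the 2020 cohort.** Let d be the share removed from the intervention arm and k the fall rate of opt-outs divided by that of stayers (assumed). With no true effect, the control arm has relative rate (1 − d) + dk and the intervention arm has 1, so the rate ratio is 1/((1 − d) + dk). With d = 0.15:

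- k = 0.5: 1/0.925 = 1.08
- k = 1: 1.00
- k = 1.5: 1/1.075 = 0.93
- k = 2: 1/1.15 = 0.87

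**2. Dilution if pooled.** Let f be the share of each arm in the 2020 cohort before removal (assumed), and c = 0.85 + 0.15k. The pooled null ratio is [0.85f + (1 − f)c] / {[0.85f + (1 − f)] × c}.

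| f | k = 0.5 | k = 2 |
|---|---|---|
| 0.10 | 1.007 | 0.989 |
| 0.30 | 1.022 | 0.965 |

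The range is about 0.97 to 1.02.

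**3. Re-entry.** From a July–October 2020 start to an April–August 2021 roll-out is 6 months (October to April) to 13 months (July to August). The 90 days before 1 April 2021 begin on 1 January 2021, after the opt-out phase closed. The look-back that defines the 2021 sample therefore falls wholly after any 2020 mailing, so eligibility at a 2020 intervention clinic can depend on that mailing. The size cannot be computed: neither the number mailed in 2020 nor the number who stopped is given. If both cohorts were analysed, the two 24-month windows for a re-entrant would overlap by 24 − 13 = 11 to 24 − 6 = 18 months, and the same falls could count twice.

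**4. Start of follow-up.** Section 2.2.d starts follow-up at mailing, while section 7.1.e bars a second mailing for the same class. For a re-entrant mailed in 2020 for their only class, the plan does not say which date starts the clock.

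**5. Extraction window.** Months available to 6/30/2022 from roll-out on the first of the month in 2020: July 24.0, August 22.9, September 21.9, October 20.9. Only a roll-out at the very start of July reaches 24 months.

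**6. Refusers.** Sections 5.3 and 7.1.k stop further data collection on people who opt out. The waiver exclusions (3.3.b) and waiver mailing rule (7.1.e) contain nothing that would keep them out.

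**The case against.** **The section 7.5 instruction may be leftover text.** The opt-out list speaks of eight clinics and twelve monthly repeats, which could not have run under a protocol that ended in October 2020, and its data window was not extended when the waiver one was. A reader might infer that the 2020 data will be pooled into the primary analysis; the documents neither state nor rule that out. But the eight-clinic wording also appears in the waiver list, so it does not mark obsolete text, and section 5.1 says the application describes both groups. The missing rule stands.

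**What is called fatal is the opt-out rate.** A reader might infer that the plan knowingly keeps a cohort it has condemned. Section 5.1 applies the phrase to the rate, as the reason for changing procedures.

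**Refusers are not shown to be re-enrolled.** That inference is tempting from section 3.3.b, but it conflicts with sections 5.3 and 7.1.k, and section 10.2.b still provides for tracking those who refuse. The supported statement is that the sections disagree.

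**The bias may be smaller.** If the 15% is of those mailed, and each clinic had two monthly mailings at the 15% cap (both assumed), 30% were mailed and 0.30 × 0.15 = 4.5% removed. The range becomes 1/1.045 = 0.96 to 1/0.9775 = 1.02. That applies if unmailed patients are analysed too; if only mailed patients contribute follow-up, 15% remains the relevant share. Only Capitol Hill is named as launched in 2020. As one of nine equal pairs (assumed, f = 1/9, d = 0.15), the pooled ratio is about 0.99 to 1.01. The effect on the whole trial is therefore likely to be modest.

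**The sample is static, and repeat mailing is barred.** Section 7.1.e says the sample is identified once. If the 2020 sample stands, the one-arm loss stays in it; if it is redrawn in 2021, re-entry applies. The bar on a second same-class mailing does not govern sample membership.

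**A short window is tolerable.** Section 2.2.d accepts 12 to 24 months with an offset, so the 6/30/2022 date contradicts section 7.5 but does not invalidate the model.

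**Conclusion.** The concern holds in a bounded form. One-arm removal after randomisation is documented, outcome extraction for that cohort is still instructed, and no rule keeps it out of the primary analysis. The waiver-phase rules, followed as written, also allow 2020 exposure to shape the 2021 sample in the intervention clinic only. This re-entry is permitted by the text, not stated as intended. The 2021 schedule numbers its clinics, so the place of Capitol Hill in it rests on the list in section 7.1.a.

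The bias is confined to the clinic pair or pairs launched in 2020. The figures of 0.87 to 1.08 (within cohort) and about 0.97 to 1.02 (pooled) rest on d = 0.15, on assumed k between 0.5 and 2, and, for the pooled range, on an assumed share of 10 to 30%. The direction is unknown. Re-entry bias is additional and cannot be sized from the documents.

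**What to change.** 1. In section 2.2.d, state that the primary analysis uses the waiver-protocol samples only, and that the 2020 opt-out data are described separately and not pooled. Bring section 7.5 and the opt-out window in section 7.3.d into line.
2. Pre-specify a sensitivity analysis of the primary outcome that omits every clinic pair launched in 2020. Step 1 alone does not remove re-entry bias; this shows how far the result depends on it.
3. Reconcile sections 5.3 and 7.1.k with sections 3.3.b and 7.1.e on whether 2020 refusers may enter the 2021 sample.

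Any exclusion of 2020 sample members must be applied identically in both clinics of a pair. Because the static sample is every eligible chronic user at the clinic, such an exclusion could remove most of the pair, so it is better run as a sensitivity analysis than imposed on the primary set.

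The cost is a few sentences, a little more analysis work and slightly lower precision in the sensitivity analysis.

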8.1 Benefits

a. Direct Benefits (For PHASE II Focus Groups):

Check boxes below for all potential direct benefits to participants.

- ☒ None
- ☐ Potential improvement in physical health due to the following:
 - ☐ Clinical intervention, such as counseling, exercise, etc.
 - ☐ Medical procedure or treatment (not including medications)
 - ☐ Administration of medication(s)
 - ☐ Other (please describe briefly):

a. Direct Benefits (PHASE III Intervention):

Check boxes below for all potential **direct** benefits to participants.

- ☐ None
- ☒ Potential improvement in physical health due to the following:
- ☐ Clinical intervention, such as counseling, exercise, etc.
- ☐ Medical procedure or treatment (not including medications)
- ☐ Administration of medication(s)
- ☒ Other (please describe briefly): | As a result of patients receiving the educational brochures and providers receiving the EBPOs, patients may achieve safer medication usage thereby reducing their risk of falls and fall-related injuries. |

b. Benefits by Population

If any of the benefits listed in above apply to only certain cases or subgroups within the study, please describe here.

| The direct benefits apply only to patients receiving care at primary care clinics randomized to be an Intervention Clinic. |

b. Indirect benefits

Check boxes below for all potential **indirect** benefits. (For PHASE II and PHASE III):

- ☒ Increase in scientific knowledge for society
- ☐ Other (please describe briefly): | |

